14.4 Oculomotor Instability (OCI)

Oculomotor Instability (OCI) will be measured with fixation and without fixation according to the imaging schedule of Section 3.5 of the SAP and Imaging Charter. The OCI values and changes from baseline for each eye (treated eye and contralateral eye) will be summarized using continuous descriptive statistics and 95% CIs by visit and eye for each dose group for all subjects. Baseline OCI is the average of all pre-dose OCI assessments. A subject listing of OCI will also be produced.

14.5 Electroretinogram (ERG) in Scotopic and Photopic Conditions

Electroretinogram (ERG) will measure a-wave (initial corneal-negative deflection) and b-wave (corneal-positive deflection) under scotopic (low light conditions or dark adaptive measures) and photopic (normal light conditions or light adaptive measures) conditions. Dark adaptive oscillatory potentials, light adaptive flicker response, overall rod and cone waves and overall rod and cone functioning will also be assessed. ERG measurements will be taken in accordance to the imaging schedule of Section 3.5 of the SAP and the Imaging Charter.

The ERG values and changes from baseline for each eye (treated eye and contralateral eye) will be summarized using continuous descriptive statistics and 95% CIs by light/dark adaptive condition, visit and eye for each dose group for all subjects. Baseline ERG is the average of all pre-dose ERG assessments for that light/dark adaptive condition. A subject listing of ERG will also be produced.

14.6 Spectral Domain Ocular Coherence Tomography (SD-OCT)

Spectral Domain Ocular Coherence Tomography (SD-OCT) will measure Full Retinal Thickness (FRT), Outer Nuclear Layer (ONL) Thickness, presence of Macular Edema, and Photoreceptor Outer Segment Layer Thickness (PROST) according to the imaging schedule of Section 3.5 of the SAP and the Imaging Charter.

Since SD-OCT is an efficacy endpoint but also a safety endpoint, this analysis will be produced primarily for the Efficacy Evaluable Population, and repeated for the Safety Population only if the Safety Population is different than the Efficacy Evaluable Population.

The SD-OCT values and changes from baseline for each eye (treated eye and contralateral eye) will be summarized using continuous descriptive statistics and 95% CIs by visit and eye for each dose group for all subjects. All measures, regardless of confidence score will be used for analyses. Baseline SD-OCT is the average of all pre-dose SD-OCT assessments if the exam was repeated. Tables will include

AESI for each visit with counts and percentages for each dose group and cohort with SD-OCT AESI according to Section 13.1.1 of the SAP. Post-BL values for individual SD-OCT parameters which are considered to have met AESI criteria will be based on determinations provided by the imaging reader.

A subject listing of SD-OCT will also be produced including an overview of SD-OCT related AESIs if reported.

14.7 Near-Infrared Auto Fluorescence (NIRAF)

Near-Infrared Auto Fluorescence (NIRAF) will measure the retained central hyper-autofluorescent island in subjects' eyes with the horizontal and vertical diameters and the overall area according to the imaging schedule of Section 3.5 of the SAP and Imaging Charter.

Since NIRAF parameters are an efficacy outcome but also represent a safety outcome, this analysis will be produced primarily for the Efficacy Evaluable Population, and repeated for the Safety Population only if the Safety Population is different than the Efficacy Evaluable Population.

The NIRAF values and changes from baseline for each eye (treated eye and contralateral eye) will be summarized using continuous descriptive statistics and 95% CIs by visit and eye for each dose group for all subjects. Baseline NIRAF is the average of all pre-dose NIRAF assessments if the exam was repeated. All measures, regardless of confidence score will be used for analyses. Tables will include NIRAF related AESIs for each visit with counts and percentages for each dose group and cohort with definition of the NIRAF related AESI according to Section 13.1.1 of the SAP. Post-BL values for individual NIRAF parameters (e.g. horizontal diameter decreased, vertical diameter increased) which are considered to have met AESI criteria will be based on determinations provided by the imaging reader.

A subject listing of NIRAF will also be produced including footnotes and superscript markers for each AESI.

15. Changes from Protocol-Stated Analyses

15.1 Analysis Populations

Safety Population

The safety population in Protocol Section 10.3 is defined as all subjects who receive any QR-110 or pre-medications required for the study. “Or pre-medications” is removed from the safety population so analyses will only contain subjects who receive the active study IVT injection.

Per Protocol Efficacy Population

The per protocol efficacy population is defined in Protocol Section 10.3, however due to the limited number of potential subjects for such a population, additional analyses on a Per Protocol population will not be conducted.

15.2 Data Analysis Conventions - Baseline

In Sections 8.12, 10.4 and in the Study Plan section of the synopsis in the protocol, baseline is referred to as the highest level of visual functioning in the case of repeat assessments, the measure reflecting the highest level of visual function will be used as baseline. Contrary to this, baseline will be measurement specific according to the current SAP Section 8.3.

16. References

17. Revision History

17.1 Revision 01

. Changes were made throughout the SAP for the following reasons:

- To align to the information found within the current version (6.0) of the protocol.
- To update the description of the analysis methods to incorporate decisions made during previous interim analysis as well as to better harmonize the SAP text to the actual outputs which have been produced.
- To add details relevant to generation of new or revised tables and listings which will be produced for final analysis, following end of study database lock.

The following table summarizes major revisions which implemented with this version.

Summary of Changes in the Statistical Analysis Plan

Section Number	Description of Change	Rationale
1	Added brief description of additional SAP prepared by Cytel, Inc. for analyses produced beyond scope of this SAP.	Comprehensive accounting of planned analyses.
2.5	Additional details for protocol defined list of endpoints were added	To enhance clarity
3.3	Update enrollment status, including no dosing at high dose	Clarify dose groups for analysis
7	Added All Enrolled Subjects Population,	Needed for analysis.
8.2 and 8.2.1		
8.3	Added “and most safety endpoints.”	Assumption was clarified.
8.4	The “combined” cohort is 1 st .	Re-organized cohort order to match with actual output.
8.5	Added “prior to the first maintenance dose of each cohort.”.	Added information to rational for DMC meetings based on Sponsor’s rational.
8.6	Second and third interim analysis paragraph added.	Added for additional interim analysis to explain rational.
10.2	Added section to explain baseline characteristics overview listing.	Added for Sponsor request analyses.
11	Ocular summaries to be produced separately for TE and CE	Sponsor requested analysis.

12	Added variable “number of doses received” and added derivation of “number of doses expected”	Sponsor requested analysis, and to provide clarification of how expected doses is derived.
13.1.1	Updated description of identification of AESI events	Updated description to match current process.
13.2-13.4	Updated description identification of specific AESI and for linking of AESI within AE data to individual examination	Updated description to match current process.
15	Updated description of analysis populations to be used for efficacy analyses. Added “responder analysis” section and tables.	Safety Population to be used only if differs from Efficacy Evaluable. Added for Sponsor request analyses.
15.1	Visual Acuity moved from Safety Section (formerly 13.2) to Efficacy Section (15.1) Updated description of AESI identification for BCVA. Added shift table for BCVA and BRVT.	BCVA is primary efficacy endpoint for analysis. To align to current process. Table was being produced, description had been omitted from SAP text.
15.6, 15.7	Added conditional rerun of results on Safety Population. Updated description identification of specific AESI and for linking of AESI within AE data to individual examination	Sponsor requested analysis. Updated description to match current process.
15.8.1	Mobility course section updated to provide additional details of testing procedure, including courses used.	To provide greater clarity of mobility course assessment.
17 and 17.1	Revision History section added	Revision History section added

21. Appendices

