### 2.3.1 Rationale for Open-label Design in Patients

Intravitreal injection is a well-established route of administration within ophthalmic indications; however, rare but potentially serious complications to IVT injections exist, including acute onset endophthalmitis, pseudo-endophthalmitis, cataract and retinal detachment. Although the risk of serious complications is small, it is well-documented ([Artunay 2009](#), [Fagan 2013](#), [Falavarjani 2013](#)). Therefore, placebo injections will not be administered in this study to preserve subject safety.

Use of sham injections to mask subjects to treatment assignment in studies of products administered via IVT injection eliminates the risk of complications due to injection in the contralateral eye. Sham injections that closely mimic the active injection can effectively mask participants to treatment assignment; however, the masking effect is less pronounced in the case where a single subject would receive both the real and sham injections, one in each of their eyes ([Glassman 2012](#)), as would be required in LCA due to the *CEP290* p.Cys998X mutation.

This study will be an open-label study and sham injections will not be used. Masking of participating subjects is of particular importance when subject effort or perception could bias evaluation of study endpoints; this is true for the assessment of subjective endpoints such as visual acuity ([Glassman 2012](#)). However, many assessments are objective tests (Pupillary Light Reflex [PLR], OCT, oculomotor instability [OCI], ERG, and infrared imaging) which are not related to subject responses. A central reading center will be used for several of the ophthalmologic assessments, including PLR, OCI, Full Field Stimulus Testing (FST), ERG, OCT and infrared imaging, which will be reviewed and interpreted by an independent masked evaluator. Mobility course scoring will also be reviewed and calculated by a masked evaluator. Furthermore, this study will evaluate safety and tolerability as the primary endpoint. Measures of safety will be monitored and severity and causality determined by the Investigator. Taken together, the risk of the introduction of bias to the determination of safety from the participant is low and sham injections will not reduce bias introduced by Investigators.

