## **10.0 STATISTICAL METHODOLOGY**

### **10.1 General Considerations**

A comprehensive Statistical Analysis Plan (SAP) specifies the statistical methodology, and table, listing and figure (TLF) formats for all aspects of the planned analyses. The SAP supports the completion of the Clinical Study Report (CSR) for this protocol. As the risk profile of QR-110 in humans is unknown and this is a first-in-human trial, all AEs will be considered in determining the safety profile of QR-110 unless obviously unrelated. As an early phase clinical study, exploratory analyses not necessarily identified in the SAP may be performed to support the clinical development program. Any p values that will be calculated according to the analysis plan will be interpreted in view of the exploratory nature of the study. Any post-hoc, or unplanned, analyses not identified in the SAP will be clearly identified in the CSR, in accordance with applicable Standard Operating Procedures (SOPs) of the sponsor.

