4.2 Replacement of Subjects

Subjects who discontinue from the study without receiving any study drug will be replaced. Subjects discontinuing the study before the full course of study drug may be replaced by a subject who will be assigned the same dose as the subject being replaced. The decision for replacement will be made by the Sponsor based on available data and perceived need for additional data.

5. Data Preparation

All reported study data will be recorded on the electronic case report forms (eCRFs)

Only the

Principal Investigator and authorized study staff according to the Delegation of Responsibilities log are entitled to make entries in the eCRF.

After data are entered into the clinical study database, electronic edit checks and data review will be performed. All data validation specifications and procedures are detailed in the Data Validation Manual as a separate document. When the database has been declared to be complete and accurate, the database will be locked. Any changes to the database after data have been locked can only be made with the approval of the Sponsor in consultation with SDC.

All analyses outlined in this document will be carried out after the following have occurred:

- All data management requirements are met according to SDC standard operating procedures, including data entry, performance of edit and validation checks, documentation and resolution of data queries, and database lock with written authorization provided by appropriate SDC and Sponsor personnel;
- Protocol deviations have been identified and status defined (major/minor deviations);
- Analysis populations have been determined.

6. Analysis Populations

The analysis population definitions in the SAP will supersede the analysis definitions in the protocol.

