7.6 Interim Analyses

An interim analysis of all outputs was conducted after the eighth subject in the study had at least 3 months of data in accordance with SAP version 1.0. The interim analysis included all available study data (all monitored and cleaned) at the time of the data snapshot, .

An additional interim analysis (interim analysis 2) of all outputs was performed using all available data (all monitored and cleaned) from all 11 subjects at the time of the data snapshot (ie, after mid-August 2018). SAP Version 1.0 was in effect at the time of this interim analysis.

A third interim analysis, consisting of all outputs produced for interim analysis #2, will be performed once the last subject has completed Visit 15 (end of study visit) and there is a soft lock. This third interim analysis (planned for August 2019) will consist of all outputs for interim analysis 2 and will include all available study data (all monitored and cleaned) at the time of the data snapshot.

No alpha or family-wise error rate adjustments are made for interim analyses at the data for this early phase 1b/2 trial as all analyses are exploratory.

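### SAP Revision 01 added a responder analysis after interim analysis 2 had covered all 11 subjects, and the CSR labelling rules as written would let it be reported as planned

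*SAP*

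**What the plan says.** Four parts of the documents bear on this.

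- **Interim looks (SAP 7.6).** Interim analysis 1 produced all outputs once the eighth subject had at least 3 months of data, under SAP 1.0. Then: "An additional interim analysis (interim analysis 2) of all outputs was performed using all available data (all monitored and cleaned) from all 11 subjects", with a snapshot after mid-August 2018 and SAP 1.0 still in force. A third look is planned for August 2019.
- **Revision 01 (SAP 17.1).** One stated reason is "To update the description of the analysis methods to incorporate decisions made during previous interim analysis". The log row for the efficacy section reads "Added “responder analysis” section and tables", with the rationale "Added for Sponsor request analyses". The row for visual acuity records its move from the safety section to the efficacy section and gives as rationale "BCVA is primary efficacy endpoint for analysis". The log's section numbers run one ahead of the body, so its Section 15 is the efficacy section, printed as 14.
- **CSR labelling.** Protocol 10.1: "Any post-hoc, or unplanned, analyses not identified in the SAP will be clearly identified in the CSR". SAP Section 1 likewise has the CSR identify only analyses additional to those in this SAP.
- **Changes from the protocol (SAP 15).** This section lists two items: analysis populations and the baseline definition.

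**The concern.** The labelling rule separates planned from unplanned analyses by asking whether they appear in the SAP. That works only if the SAP predates the data. Here it was revised after an all-output look at every subject in an open-label study, and the revision brought in a new analysis. Once written in, that analysis meets the literal test for being planned.

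This matters more for a responder analysis than for most additions. A responder rule involves choices of measure, cut-off and eye. With 11 subjects, each subject moves the rate by 1/11, about 9 percentage points, so a rule set with results in view can produce an apparent response rate from noise. A CSR reader who is not told when the rule was set cannot allow for that.

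**Working it through.** The plan gives no alpha, power or effect size, and its sample size is not power-based, so there is no figure to reproduce. The check is of dates and wording, followed by an illustration of scale.

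**Order of events**

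1. Protocol version 6.0 is dated 02-Aug-2018 (SAP Section 1).
2. The interim 2 snapshot falls after mid-August 2018: all outputs, all 11 subjects, SAP 1.0 (SAP 7.6).
3. Revision 01 reports interim 2 in the past tense, and its log records that the paragraph describing it was added. It is therefore later than interim 2.
4. The same text treats the August 2019 look as still to come, so Revision 01 lies between the two. Its exact date is not visible.

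**Was the sponsor aware of the results?** No sentence says so. Three statements point that way: the revision incorporates decisions made during an interim analysis (SAP 17.1), the high dose was not opened because of interim results (SAP 2.3), and efficacy review was to be continuous (Protocol 10.9). Treatment was not masked (SAP 4.1), although central graders were masked to which eye was treated.

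**The labelling test applied to the responder analysis**

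| Rule | Test | Result |
|---|---|---|
| Protocol 10.1 | Absent from the SAP? | No, Revision 01 contains it; no flag required |
| SAP Section 1 | Additional to this SAP? | No; no flag required |
| SAP Section 15 | Listed as a change from the protocol? | Not listed |

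**Illustration of scale.** The responder rule is not visible, so all inputs here are assumptions except the 11 subjects and the five secondary efficacy measures (BCVA, red FST, blue FST, white PLR amplitude, white PLR latency; Protocol 4.1.2). Changes are standard normal with no treatment effect. Correlation is 0.5 between eyes and 0 to 0.6 between measures. A responder is an eye whose change exceeds a cut-off *c*, and

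D = (treated-eye responders − contralateral-eye responders) / 11.

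Each set has three cut-offs, in SD units: 0.5/0.84/1.28, 0.5/1/1.5 or 1/1.5/2, with 40,000 simulated trials per setting. A difference of 3/11 is 27 percentage points.

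| How the rule is set | Mean of D, in points | Chance that D ≥ 3/11 |
|---|---|---|
| Fixed in advance, c = 1 SD | 0 | about 4% |
| Best of 3 cut-offs, one measure | about +6 to +8 | about 5% to 12% |
| Best of 5 × 3 = 15 rules | about +15 to +23 | about 18% to 46% |

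Lower cut-offs take the last chance up to about 55%. The last row is a worst case: it assumes that the most favourable of all 15 rules was picked, on the same data that are then reported. Interim 2 had incomplete 12-month follow-up, so later data would dilute the effect.

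**The case against.** The strongest reply is that nothing is hidden and nothing confirmatory is claimed. The log discloses the addition, and SAP 7.6 states which SAP version was in force. All analyses are called exploratory, this SAP plans no inferential tests, and the study is not powered for efficacy. The stated reason for the responder tables is sponsor request, the same reason given for a baseline listing, and no text ties them to interim findings. The sentence about interim decisions also goes on to cite harmonising the SAP with outputs already produced. The responder section itself is not visible and may carry its own label.

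Most of this is fair, and it limits the point to labelling. It does not remove it: a change log in the SAP is not a statement in the CSR, and exploratory results still need their provenance stated.

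Three stronger readings are tempting, and the documents do not support them.

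- **That Revision 01 made BCVA the primary efficacy endpoint, and that Protocol 10.1 would let the CSR say so.** The recorded change is a section move. The primary label is a rationale remark worded as existing fact, and when it was adopted is unknown. SAP 1.5 still ranks BCVA as secondary, and protocol version 6.0, dated before the interim 2 snapshot, already lists it as a secondary efficacy evaluation (10.8). Protocol 10.1 governs unplanned analyses, not endpoint rank.
- **That the third look, at soft lock, breaches SAP Section 5.** That section does say "All analyses outlined in this document will be carried out after the following have occurred" and includes database lock. But SAP 7.4 requires a locked database for analyses after study completion, and SAP 7.6 specifically provides for this look at soft lock on monitored, cleaned data.
- **That the chance of a false positive across five endpoints measures this defect.** At 5% each and independent, it is 1 − 0.95^5 = 22.6%, but that is ordinary multiplicity. It would be the same without Revision 01, and SAP 7.7 discloses that no adjustment is made.

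**Conclusion.** The point holds for the responder analysis. It was first documented in the SAP after an all-output interim look at all 11 subjects, and neither CSR labelling rule, read literally, would mark it as such. This rests on the order of events in SAP 7.6 and 17.1, which is clear, and on the wording of Protocol 10.1 and SAP Section 1, which name no SAP version or date. Awareness of the results is a strong inference only. The documents do not show that the responder rule was chosen to fit the data, and the simulated figures are not evidence that it was. They show only that selection at this sample size could add roughly 6 to 8 points with a free cut-off, and 15 to 23 with a free measure as well. The BCVA remark is a minor inconsistency with SAP 1.5.

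**What to change.** 1. In SAP Section 15 and in the CSR, state that Revision 01 postdates interim analyses 1 and 2, and that any analysis first documented after SAP 1.0 is labelled *defined after interim data were available*. Say that this overrides the wording of Protocol 10.1.
2. List the responder analysis there by name.
3. Report responder results for both the treated and the contralateral eye.
4. Remove the remark that calls BCVA the primary efficacy endpoint, or reconcile it with SAP 1.5.

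The cost is wording and table presentation, with no new data. Claims based on responder rates become more cautious.

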21.1 Appendix 1: Table of Equivalency – Visual Acuity

Visual Acuity	Snellen Notation	Decimal Fraction = Monoyer Scale	LogMAR = ETDRS Notation = Study Notation	Equivalence BRVT test
Light Perception				
Visual Acuity at 60 cm = 2 feet				
Hand motion¹⁰	20/20000	0.001	+3.00	
	20/16000	0.00125	+2.9	
			+2.7	
	20/8000	0.0025	+2.6	
			+2.5	
			+2.4	
	20/4000	0.005	+2.3	
			+2.2	
Counting Fingers¹⁰	20/2000	0.010	+2.00	STE 100M
	20/1600	0.0125	+1.9	STE 25M
	20/1200	0.016	+1.8	
	20/1000	0.020	+1.7	
Visual acuity at 1m	20/800	0.025	+1.6	STE 40M
	20/600	0.033	+1.5	
	20/500	0.04	+1.4	STE 25M
	20/400	0.05	+1.3	
	20/320	0.063	+1.2	
	20/250	0.08	+1.1	
Visual Acuity at 4 m	20/200	0.10	+1.00	
	20/160	0.125	+0.9	
	20/125	0.16	+0.8	
	20/100	0.20	+0.7	
	20/80	0.25	+0.6	
	20/63	0.32	+0.5	
	20/50	0.40	+0.4	
	20/40	0.50	+0.3	
	20/32	0.63	+0.2	
	20/25	0.80	+0.1	
	20/20	1	0	
	20/16	1.25	-0.1	
	20/12.5	1.6	-0.2	
	20/10	2	-0.3	

References: Bailey 1976; Bainbridge 2008; Ferris 1982; Ghazi 2016; Holladay 1997; Holladay 2004; Lange 2009; Maguire 2008; Schulze-Bonsel 2006; Simonelli 2010; Sloan 1951

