14.1 Visual Acuity (BCVA) with ETDRS and BVRT

The logarithm of the minimum angle of resolution (logMAR) visual acuity is assessed using an EDTRS chart according to Section 3.5 of this SAP. Light perception (LP), detection of hand movement (HM) and ability to count fingers (CF) are also acceptable measures of visual acuity for this study. The Berkeley Rudimentary Vision Test (BVRT) will also be used to assess subjects' visual acuity. Since BCVA is an efficacy endpoint but also a safety output, this analysis will be produced primarily for the Efficacy Evaluable Population, and only repeated for the Safety Population if the Safety Population is different than the Efficacy Evaluable Population.

The observed value and change from baseline visual acuity will be summarized for each eye (treated eye and contralateral eye) for BCVA using continuous descriptive statistics on the logMAR scale by visit for each dose group and for all subjects. If there is no logMAR evaluation available from the EDTRS chart or BVRT assessment, visual acuity measures of LP, HM, and CF will be summarized using the following logMAR equivalents (refer to Section 21 Appendix 1 for full table):

- Light Perception = 4.0 logMAR
- Hand Movement = 3.0 logMAR
- Count Fingers = 2.0 logMAR

BVRT will be summarized in a similar manner as described for BCVA via ETDRS, with discrete summary statistics for frequency of Light Perception, Black White Discrimination, White Field Projection, and Cord Pair. The BVRT logMAR value will be summarized with continuous descriptive statistics. For BVRT, if the Light Perception question is not answered on the eCRF, then values will be imputed from the corresponding Best Corrected Visual Acuity (BCVA) Light Perception answer.

BCVA related AEs of special interest (AESI) will also be summarized with counts and percentages for each dose group and cohort with the definition of the BCVA related AESI according to Section 13.1.1 of the SAP. BCVA related AESI will include those TEAEs with MedDRA PTs of 'visual acuity reduced' or 'blindness'. In order to establish if results at individual visits resulted in an AESI report or not, the onset date of each reported AESI related to BCVA will be compared to dates of BCVA assessments, and assessments with dates between the onset date and resolution of the corresponding AESI will be flagged as having led to an AESI report.

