A subject listing of visual acuity will also be produced. This BCVA listing will include a variable that indicates if a subject had a visual acuity change from baseline of ≥ 0.3 (15-letters or more) on the logMAR scale.

Shifts from baseline to post-BL in vision category will be summarized for BCVA using categories of LP, HM, CF and logMAR BCVA (i.e. visual acuity reported as better than CF), and for BRVT using categories of light perception, black white field discrimination, white field projection and logMAR BRVT (i.e. visual acuity better than light perception).

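### SAP Appendix 1 gives the BRVT card STE 25M two logMAR equivalents, +1.9 and +1.4; the +1.9 entry fits no distance in the table and could misstate acuity by up to 0.5 logMAR if the table is used to convert cards

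*SAP*

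**What the plan says.** SAP Appendix 1 (Section 21.1) sets Snellen, decimal and logMAR values side by side and has a last column for the equivalent BRVT card. Four rows carry a card, in this order:

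- "20/2000 0.010 +2.00 STE 100M"
- "20/1600 0.0125 +1.9 STE 25M"
- "20/800 0.025 +1.6 STE 40M"
- "20/500 0.04 +1.4 STE 25M"

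SAP 14.1 makes the BRVT logMAR an analysed variable: "The BVRT logMAR value will be summarized with continuous descriptive statistics". (The SAP spells the test both BVRT and BRVT; I use BRVT.) The same section ranks a BRVT logMAR with an ETDRS one, ahead of the light perception, hand movement and count fingers substitutes: "If there is no logMAR evaluation available from the EDTRS chart or BVRT assessment, visual acuity measures of LP, HM, and CF will be summarized". It points to the appendix in that sentence on substitutes: "refer to Section 21 Appendix 1 for full table". The BCVA listing is to mark any "visual acuity change from baseline of ≥ 0.3 (15-letters or more) on the logMAR scale".

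**The concern.** One card has two equivalents half a logMAR unit apart, and nothing in the table tells the user which to take. The appendix is the only card-to-logMAR conversion in the two documents, and BRVT logMAR can stand as a subject's acuity value. If cards are converted with it, a reading given the +1.9 row would make the eye look much worse than a reading given the +1.4 row, for the same card. In a study with cohorts of as few as 2 subjects, one such reading would be visible in a cohort mean and could trigger or hide the 0.3 logMAR flag.

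**Working it through.** **Inputs.** The four card rows and the distance headings (60 cm, 1 m, 4 m) are from SAP Appendix 1. The letter scale, 0.3 logMAR = 15 letters, is from SAP 14.1. Baseline BCVA as the average of Screening and Day 1 is from SAP 7.3. The minimum of 2 subjects per cohort is from SAP 2.3, and the total of 11 subjects from SAP 7.6.

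**Assumption.** The documents give no card formula. I take logMAR = log10(M / d), with M the card size and d the test distance in metres.

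**Step 1: are the logMAR figures right for their rows?** Snellen 20/x gives log10(x/20) and a decimal gives -log10(decimal). For 20/1600, log10(80) = 1.903; for 20/500, log10(25) = 1.398. All 22 rows from 20/20000 to 20/40 with both notations agree with the printed logMAR to one decimal. So +1.9 and +1.4 are correct for their rows, and the doubt lies in the card label.

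**Step 2: do the card labels reproduce?**

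| Card | Printed | 60 cm | 1 m | 4 m | Distance needed for the printed value |
|---|---|---|---|---|---|
| 100M | 2.00 | 2.22 | 2.00 | 1.40 | 1.00 m |
| 25M | 1.9 | 1.62 | 1.40 | 0.80 | 25 / 10^1.9 = 0.31 m |
| 40M | 1.6 | 1.82 | 1.60 | 1.00 | 1.00 m |
| 25M | 1.4 | 1.62 | 1.40 | 0.80 | 1.00 m |

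Three entries fit 1 m. The 25M entry at +1.9 fits none of the three distances. As read, its row falls in the block headed 60 cm, but so does the 100M row, which fits 1 m and not 60 cm. The block headings therefore do not supply the card distance.

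**Step 3: order.** At any one distance a smaller card means a better acuity, that is, a lower logMAR. Down the column logMAR falls, but the cards run 100M, 25M, 40M, 25M. The +1.9 entry breaks the sequence. At 1 m a value of 1.9 would need a card of 10^1.9, about 79M; the documents do not show which card was meant.

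**Step 4: size.**

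- Gap between the two equivalents: 1.9 - 1.4 = 0.5 logMAR; 0.5 x 15/0.3 = 25 letters, above the 15-letter flag.
- One post-baseline reading wrong by 0.5 moves a visit mean by 0.5/2 = 0.25 with 2 subjects, 0.5/5 = 0.10 with 5, and 0.5/11 = 0.045 with 11.
- One wrong reading of the two that make up a baseline moves that subject's baseline by 0.5/2 = 0.25.
- If 25M were always looked up as +1.9, a move from the 40M to the 25M card would show as 1.9 - 1.6 = 0.3 worse, which meets the flag. By the 1 m values it is 1.4 - 1.6 = -0.2, an improvement.

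**The case against.** The strongest objection is that no route into the results is shown. SAP 14.1 cites the appendix for light perception, hand movement and count fingers, not for BRVT cards, and it mentions BRVT items answered on the eCRF. If the logMAR is entered directly, a wrong label in the appendix changes nothing. This stands, and it makes the effect conditional. A reader might infer that BRVT values in the database are wrong; the documents do not show that.

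Second, one card may properly have two logMAR values at two distances. That is true in principle. At 60 cm the +1.9 row would be 1.9 - 1.62 = 0.28 off. At 25 cm, a distance the table does not print, 25M gives 2.00 and the row would be 0.1 off. So 0.5 is the upper case, for a card read at 1 m; the 4 m block carries no card. But no printed distance yields 1.9, and without a test distance per card the user cannot choose between the rows.

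Third, a single programmed lookup would not convert the same card two ways at different visits. That is fair. A lookup that consistently took the +1.9 row would still distort changes between cards, as Step 4 shows.

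Fourth, the table was read from PDF by a program. A shifted cell would not create a second 25M entry, but a misread digit could, so the page must be checked first.

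Three further readings are tempting but not supported:

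- That the table affected which eye was treated. The investigator chose the worse eye at Screening, this SAP revision postdates interim analyses that covered all 11 subjects (SAP 7.6), and nothing shows that sites used the appendix for the choice.
- That BRVT readings are common here. Eligibility extends down to light perception (protocol 5.3.1), but no count is given of subjects who needed BRVT or read a 25M card.
- That the main efficacy result is at stake. Only a rationale entry in the SAP revision table describes BCVA as primary for efficacy. SAP 1.4 and 1.5 make ocular adverse events the primary endpoint and BCVA one of several secondary endpoints, and this SAP's analyses are descriptive.

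**Conclusion.** The inconsistency is real: the appendix, as read, gives STE 25M two equivalents, and the +1.9 entry is the one that does not fit. Its effect on the data is unproven. If BRVT logMAR is derived from this table, a reading assigned to the +1.9 row could be off by up to 0.5 logMAR (25 letters), enough to cross the SAP's own 0.3 flag and to move a visit mean by 0.25 with 2 subjects or about 0.045 with 11. If the logMAR is entered directly on the eCRF, the fault stays in the appendix.

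This rests on three assumptions: that logMAR equals log10(M/d), which three of the four entries bear out at 1 m; that cards were read at up to 1 m; and that the printed label is not an extraction fault. The point is worth correcting before the final analysis because the check is cheap, not because harm has been shown.

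**What to change.** 1. Check the +1.9 row against the source page of the SAP and against the BRVT card set, then correct or delete its STE 25M entry. The documents do not identify the right card, so it should not be guessed.
2. State the test distance for each card in Appendix 1.
3. State in SAP 14.1 whether BRVT logMAR is entered on the eCRF or derived and, if derived, from what.
4. Check stored 25M readings, and any value taken from the +1.9 row. Re-derive only those converted with the wrong row, where card and distance were recorded. Values entered directly and correctly need no change.

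The cost is a one-row correction, two short statements in the SAP and a check of a limited set of readings. No new data are needed if card and distance were captured; where they were not, the affected readings should be identified as unresolved in the listing.
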